4. STUDY POPULATION

Sixty patients affected by bilateral OAG, between the ages of 20 and 70, will be enrolled in the study within a maximum time frame of 12 months (see point 9.1 "sample size").

4.1 Inclusion criteria:

- Age between 20 and 70 years old
- Diagnosis of glaucoma. Glaucoma is defined as: glaucomatous damage of the CV (Humphrey 24-2 standard SITA with mean deviation between -6 and -25 dB) and glaucomatous appearance of the optic nerve
- Visual acuity not less than 5/10

- Eye pressure below 21 mmHg with the use of ocular hypotonizing drugs including sympathomimetics, beta-blockers, prostaglandins, beta-adrenergics, carbonic anhydrase inhibitors. Such drugs can be used both alone and in combination with each other.
- Documented post-retinal nerve conduction delay through simultaneous recording of VEP and PERG showing an increase in RCT

4.2 Exclusion criteria:

- Ocular surgery in the 3 months preceding the study, including surgery for cataracts in the previous three months.
- Cataract or maculopathy
- Argon laser trabeculoplasty (ALT) within the previous 6 months
- Known hypersensitivity to the study product
- Secondary causes of ocular hypertension, including systemic or topical use of steroids
- Positive history of ocular or systemic diseases that could preclude enrollment in the study in the opinion of the investigators
- Changes in systemic therapies that could compromise intraocular pressure values (beta-blockers, alpha and beta adrenergics, calcium inhibitors, ACE inhibitors) in the 30 days prior to enrollment
- Ongoing therapy with vasoactive cerebral drugs, neurotrophic, lutein, zeaxanthin, retinal, acid, docosahexaenoic, Ubiquinone and / or its derivatives, Citicoline and / or its derivatives (possible previous treatment with Ubiquinone, L-Carnitine, Citicoline and / or its derivatives must have been suspended at least 6 months prior to inclusion in the study)
- Pregnancy, breastfeeding
- Diabetes
- Systemic lupus erythematosus, rheumatoid arthritis, connectivitis
- Concomitant use of anticoagulants and lithium

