5. EXPERIMENTAL DESIGN

5.1 Experimental plan

A prospective, multicentre, randomized, blinded, masked study that involves the enrollment of a minimum of 60 (see sample size in paragraph 9 "Statistical Analysis") affected by OAG.

Patients selected according to the inclusion / exclusion criteria, after signing the informed consent, will be randomized into two groups:

a) In a group of patients with OAG, **Citicoline in oral solution (10 ml / day, Neurotidine®)** will be administered for 12 months (Citicoline Treated Group, TC Group)

b) in another group of patients with OAG will be **administered Placebo** (Containing all excipients of Neurotidine ®) (10 ml / day) for 12 months (Placebo Treated Group, TP Group)

Randomization will be done by dividing the selected patients into two groups based on similar characteristics of: age, perimetric defect and, mainly, RCT values.

Patients will be assigned to each group by an investigator not involved in functional and structural

testing.

The key will be opened only at the end of the treatment in order to evaluate the first effects.

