5.4 Planned visits

The visits will be performed at T0 (screening), at T1 (baseline, 7-15 days after T0), after 6 months (T2) and after 12 months (T3) of follow-up not knowing which group the subject belongs to.

After screening (T0), enrolled patients will perform a baseline visit (T1) during which they will be randomized to one of the two groups. The visits will take place 6 and 12 months after the baseline visit.

A complete eye examination will be performed at T0, T1, T2 and T3 including the following assessments: corrected visual acuity, biomicroscopy, indirect ophthalmoscopy, intraocular pressure measurement with Goldmann applanation tonometer, CV test, recording of PERGs and VEPs, imaging of the optic nerve and retinal nerve fiber layer by OCT. Neuroradiological evaluation will also be performed at T1 and T3.

At the end of the T1 visit, the patient will be given 4 bottles containing 500 ml Neurotidine® or Placebo and will be given the relative instructions for administration. The regimen will be 1 administration of 10 ml once a day for 6 months. Each bottle can be used for 50 days. At the end of the 6 month period the patient will be asked to hand over the used bottles.

After 6 months \pm 10 days (T2), patients will be given an additional 4 bottles containing Neurotidine® or Placebo and will be given instructions for their administration. The regimen will be 1 administration of 10 ml once a day for 6 months. Each bottle can be used for 50 days. Again at the end of this 6 month period the patient will be asked to hand over the used bottles.

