6. ASSIGNMENT AND MASKING

Patients with OAG will be selected from a large cohort of already known diseases and followed at our facility for at least 12 months.

Only patients who meet the inclusion criteria will be selected. Patients will undergo a baseline screening visit during which conditions corresponding to the inclusion criteria will be assessed and the study will be proposed.

Only after the signing of the informed consent, a single investigator ("enrolling physician"), not involved in the clinical and instrumental evaluations, will decide whether to assign the selected patient to one of two groups: treated-Citicoline or treated-Placebo.

The assignment to one or the other group will take place in sequential order of presentation of the patient (with a 1: 1 probability of joining one or the other group) in order to constitute two homogeneous groups in number.

The aforementioned assignment will not be known to the patient and will not be known to the "enrolling physician".

Consequently, during the entire duration of the study (both at the baseline visit and at the 6 and 12 month visit), all evaluations foreseen by the study will be carried out by investigators who will not know whether the patient being examined belongs to the Citicoline-treated group or treated-Placebo.

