9. STATISTICAL ANALYSIS

9.1 Sample size

As already highlighted, the main measure on which we relied for the calculation of the sample size is the RCT.

Our aim is to evaluate the value of the RCT parameter in the group treated with Neurotidine®, compared to that of the group treated with placebo.

We consider the following RCT values: at baseline 70.21 ± 9.12 ms and at the end of treatment 63.3 ± 8.15 ms (19), with an α error of 5% and a power of 80%.

We obtain 27 participants to which we add a drop-out equal to 10%, so the final value is 30 for each group.

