9.2 General methodology

The data of each group, obtained from the PEV, PERG, CV, OCT and RM measurements will be represented by their mean and standard deviation, after having verified their normal distribution by means of the Anderson-Darling and Kolmogorov-Smirnov tests.

For each group, any variations in the measurements indicated above will be evaluated by means of a t-test for paired data.

Furthermore, the parameters of the electrophysiological, morphological and MRI measurements related to the two groups will be compared pre and post treatment, by means of ANOVA with correction of multiple comparisons based on Tukey's method.

The functional electrophysiological parameters (PEV and PERG) will be correlated by Pearson's test with the morphological OCT ones.

Finally, the possible relationship between the PEV, PERG and functional RM parameters of connection of the networks will be assessed using Pearson's test.

This analysis will be repeated respectively between the PEV and PERG parameters and the RM parameters in diffusion for each area indicated in paragraph 5.6.

The p-value of less than 5% is considered significant for any previously exposed test.

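### Section 9.2 compares the arms by a pre/post ANOVA with no covariate, although RCT is measured before treatment and 5.1 says the groups are formed mainly on RCT

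*Protocol*

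**What the plan says.** **Analysis.** Section 9.2 states for the between-group comparison that "the parameters of the electrophysiological, morphological and MRI measurements related to the two groups will be compared pre and post treatment", by ANOVA with Tukey's correction. It names no covariate, and does not say which visit supplies the pre-treatment value or which the post-treatment value. It also plans a paired t-test within each group. The ANOVA sentence does not list the visual field.

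**Measurements.** Section 5.4: "A complete eye examination will be performed at T0, T1, T2 and T3 including the following assessments", and the list that follows includes PERG, VEP, OCT and the visual field. RCT is therefore available twice before any product is given. Sections 5.2 and 5.4 call T0 screening and T1 baseline, 7 to 15 days later, with randomization at T1. MRI is done at T1 and T3 only.

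**Entry.** Section 4.1 requires "Documented post-retinal nerve conduction delay through simultaneous recording of VEP and PERG showing an increase in RCT".

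**Allocation.** Section 5.1 divides patients into groups "based on similar characteristics of: age, perimetric defect and, mainly, RCT values". Section 6 instead assigns them in the order in which they present, "with a 1: 1 probability of joining one or the other group", and names no balancing factor.

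**The concern.** A variable that matters enough to form the groups on normally belongs in the model. If allocation forces the arms to be alike on baseline RCT, the true chance variation of the treatment difference shrinks. A test that omits baseline RCT still computes its standard error as if the arms could differ freely. The reported error is then too large, the interval too wide and the p-value too high. Even without balancing, baseline RCT probably predicts 12-month RCT, and leaving it out discards information already collected.

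At stake is the precision of the primary result in a trial of 30 patients per arm. The error is towards missing an effect, not towards a false positive.

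**Working it through.** **Inputs from the protocol.** Section 9.1 gives RCT 70.21 ± 9.12 ms at baseline and 63.3 ± 8.15 ms at the end of treatment, alpha 5% and power 80%. Section 6 gives 1:1 allocation. The difference is 70.21 − 63.3 = 6.91 ms. The pooled SD is √[(9.12² + 8.15²)/2] = 8.65 ms.

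**Assumed.** The correlation r between visits is not in the protocol; 0.3 to 0.8 is shown. Variance is taken as equal at all visits, with one RCT value per patient per visit.

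**Step 1: the plan's own figure.** The protocol states: "We obtain 27 participants to which we add a drop-out equal to 10%, so the final value is 30 for each group". For an unadjusted two-sided comparison of two means, n per arm = 2 × [SD × (1.960 + 0.842) / 6.91]².
- SD 8.65 gives 24.59, so 25 (26 by the t distribution).
- SD 9.12 gives 27.34, so 28 (29 by the t distribution).
- Allowing for drop-out, 27/0.9 = 30.

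The stated 27 lies between these results, so it is consistent with an unadjusted comparison. Power at 27 per arm is 0.835 with SD 8.65 and 0.795 with SD 9.12.

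**Step 2: standard error of the between-arm difference at 27 per arm.** The unadjusted value is 8.65 × √(2/27) = 2.35 ms. Multiply by √[2(1 − r)] for a change from T1, or by √(1 − r²) for ANCOVA on T1. Normal-approximation power is in brackets.

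| r | T3 unadjusted, ms | Change from T1, ms | ANCOVA on T1, ms |
|---|---|---|---|
| 0.3 | 2.35 (0.835) | 2.79 (0.699) | 2.25 (0.868) |
| 0.5 | 2.35 (0.835) | 2.35 (0.835) | 2.04 (0.924) |
| 0.7 | 2.35 (0.835) | 1.82 (0.966) | 1.68 (0.984) |
| 0.8 | 2.35 (0.835) | 1.49 (0.996) | 1.41 (0.998) |

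**Step 3: what balancing does to the test.** In a simulation, 54 patients were ranked on baseline RCT and paired, and one of each pair was allocated at random to each arm (4,000 runs). Section 5.1 does not say how balance is reached; pairing gives nearly perfect balance, so these results are near the extreme. The nominal level is 0.05, with simulation error √(0.05 × 0.95/4000) = 0.003.

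| r | Type I error: T3 unadjusted | Change | ANCOVA | Power: T3 unadjusted | Change | ANCOVA |
|---|---|---|---|---|---|---|
| 0.5 | 0.027 | 0.027 | 0.057 | 0.859 | 0.865 | 0.915 |
| 0.7 | 0.008 | 0.038 | 0.053 | 0.891 | 0.970 | 0.980 |
| 0.8 | 0.002 | 0.039 | 0.052 | 0.925 | 0.997 | 0.998 |

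**Step 4: does averaging T0 with T1 add much?** With equal correlations, the ANCOVA residual variance is 1 − r² on T1 alone and 1 − 2r²/(1 + r) on the two-visit mean. At r = 0.7 these are 0.51 and 0.42, or 1.68 and 1.53 ms. Power at SD 8.65 rises from 0.868 to 0.885 (r = 0.3), from 0.924 to 0.949 (r = 0.5) and from 0.984 to 0.995 (r = 0.7). The gain over T1 alone is at most about 2.5 percentage points.

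**The case against.** **Covariates are often left to a statistical analysis plan.** This is true, and it limits the severity. But section 9.2 is not silent: it names the between-group method, and that method omits the factors that 5.1 puts first.

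**The ANOVA may be a group-by-time model, which uses the pre-treatment value.** This stands in part. With two time points, the interaction test is the same as a t-test on the change, so baseline RCT would not be ignored. The wording does not settle which model is meant. The comparison with the change score in step 2 covers this reading: the gain from ANCOVA is then 0.31 ms at r = 0.5 but only 0.14 ms at r = 0.7.

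**Balancing may not take place.** Sections 5.1 and 6 contradict each other. Under section 6 alone, the loss of type I error in step 3 does not arise, but the gain in precision in step 2 remains.

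**Stronger readings that a reader might infer.**
- *That a duplicate baseline from a run-in is being wasted.* No run-in is described. T0 is screening and T1 is baseline, so T1 is the natural pre-treatment value. Not analysing a screening recording is ordinary practice.
- *That selection on high RCT biases the treatment comparison.* Regression to the mean acts in both arms and does not bias a randomized contrast. The eligibility row in section 5.2 is ticked at all four visits, so it does not show a second RCT selection at T1.
- *That averaging the two visits cuts the variance by 29% (0.60 to 0.42; 1.82 to 1.53 ms).* This compares with a change score, which 9.2 does not specify. About half of the fall, 1.82 to 1.68 ms, comes from ANCOVA on T1 alone.

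**Conclusion.** The point holds as a matter of analysis choice. Section 9.2 fixes a between-group comparison without adjustment for RCT, age or perimetric defect, while 5.1 says that the groups are formed on them. For r between 0.3 and 0.8, ANCOVA on one baseline lowers the standard error from 2.35 ms to between 2.25 and 1.41 ms against an unadjusted T3 comparison. Against a change from T1, it lowers it from 2.35 to 2.04 ms at r = 0.5 and from 1.82 to 1.68 ms at r = 0.7. If allocation does balance closely on RCT, the unadjusted test works well below its nominal 5%.

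The severity is moderate. The sample size is consistent with an unadjusted test, and power at the assumed effect is 0.80 to 0.84 without adjustment, so the documents do not support calling the trial underpowered for want of a covariate. The exact gain depends on a correlation that the protocol does not give.

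**What to change.** In section 9.2:
- Name the T1 value as baseline and T3 as the time of the primary comparison.
- Compare T3 RCT between arms by ANCOVA on baseline RCT, with age and perimetric defect (mean deviation) as further covariates.
- Treat the OCT outcomes in the same way, and the MRI outcomes with their T1 baseline.

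Reconcile sections 5.1 and 6 on whether allocation balances on age, perimetric defect and RCT. The covariates in 9.2 should then match the rule that is kept.

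Using the mean of T0 and T1 as the ANCOVA covariate is optional and adds little. T0 is the screening value selected for high RCT, so it should not serve as the pre-treatment value in the within-group paired tests, where a fall on re-measurement would look like improvement.

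The cost is a change of wording before the treatment key is opened, with no new visit or measurement. With 54 patients, a model with an intercept, treatment and three covariates leaves 54 − 5 = 49 residual degrees of freedom, a negligible loss.

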2. OBJECTIVES AND AIMS OF THE STUDY

- 1) Primary Objective: to evaluate whether treatment with **Citicoline in oral solution** can produce an improvement of the post-retinal nerve conduction, altered base in patients with OAG.
- 2) Secondary objective: to evaluate in patients with OAG whether the possible changes in post-retinal nerve conduction induced by treatment with Citicoline in oral solution (information obtained through electrophysiological recordings) are associated or not with **morphological and functional variations of the nervous structures that form the optical pathways** (NGL, optic tract, visual cortex, information obtained through the acquisition of structural and functional magnetic resonance imaging) and whether both conditions can be related to the morpho-functional variations of the RGCs and of the visual field (CV).

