5.6 Efficacy parameters

- 1) For the evaluation of the RCT, the difference of the latency time P100 of the PEV and the latency time P50 of the PERG will be considered.
- 2) For the assessment of the visual field (HFA 24-2 and 10-2), the following will be considered: MS, MD and PSD.
- 3) The following parameters will be recorded for each SD-OCT imaging session:
 - the average thickness of the layer of the peripapillary retinal nerve fibers and the thickness divided by sectors.
 - the average thickness of the neural rim and the thickness divided by sectors
 - the average thickness of the ganglion cell layer and the internal plexiform layer (GCL / IPL) and the thickness divided by sectors
- 4) For each diffusion-weighted MRI acquisition, the following parameters of the thalami and LGN and of the optical tracts will be acquired: fractional anisotropy (FA), average diffusivity (MD, axial (AD) and radial (RD)).
For each acquisition of morphometry based on the voxel, the neuronal density of all cortical areas of the entire brain will be acquired.
For functional MRI at rest, the connectivity strength (Z-score) of all the independent cortical networks (linked to vision and not, independently) will be analyzed, as well as the degree of functional

connectivity between the thalami and the LGN and RSNs detected in the previous independent analysis.

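### Section 9.2 compares the arms on many MRI parameters with Tukey's method as the only correction, which leaves the family-wise error across those parameters uncontrolled

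*Protocol*

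**What the plan says.** The secondary objective in section 2 names three targets for imaging: "NGL, optic tract, visual cortex, information obtained through the acquisition of structural and functional magnetic resonance imaging".

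Section 5.6 casts the net wider:
- Diffusion: four indices (fractional anisotropy, and mean, axial and radial diffusivity), for which "parameters of the thalami and LGN and of the optical tracts will be acquired".
- Morphometry: "the neuronal density of all cortical areas of the entire brain will be acquired".
- Resting-state functional MRI: "the connectivity strength (Z-score) of all the independent cortical networks (linked to vision and not, independently) will be analyzed", plus connectivity of the thalami and LGN with each network found.

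Section 9.2 sends all of this into the comparison of the arms. It says that "the parameters of the electrophysiological, morphological and MRI measurements related to the two groups will be compared pre and post treatment". The method is an analysis of variance, and the only multiplicity correction that the section names is Tukey's. The section closes with a general rule: "The p-value of less than 5% is considered significant for any previously exposed test". Sections 5.2 and 5.4 place MRI at T1 and T3 only.

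The protocol names no main MRI parameter and no order among regions. It gives no correction across regions, indices or networks, and does not call any MRI result exploratory.

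**The concern.** Two kinds of multiplicity arise here. One lies within a parameter: two arms at two times give four means and six pairwise contrasts. The other lies across parameters: the same comparison is repeated for every index, area and network. Tukey's method deals with the first and takes no account of the second.

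Section 9.2 names only Tukey and sets 5% for every listed test. Followed as written, it would call a chance difference between the arms in any one area or network significant, including areas unrelated to vision. Such a difference could then be reported as a structural or functional effect of citicoline.

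**Working it through.** The protocol gives no family-wise error figure to reproduce, so the check starts from its counts.

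**Inputs**
- Diffusion parameters (section 5.6): 4 indices × 3 structures = 12. Keeping left and right separate gives 24; the split by side is an assumption.
- Cortical areas and networks: no number is given. I use 100 areas as an assumption, with 50 as a lower value.
- Threshold (section 9.2): p < 0.05 for any test.
- MRI times: T1 and T3, so 2 arms × 2 times = 4 means per parameter.
- Evaluable patients (section 9.1): 27 per group. This is used only for Tukey's degrees of freedom, 4 × (27 − 1) = 104, treating the four arm-by-time cells as independent.
- Correlation between parameters: not given. I use 0 and 0.7, the same for every pair, as assumptions.

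**Error per arm contrast**

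Two readings of section 9.2 are possible.
1. One arm contrast per parameter. Tukey then has a single pair to compare and changes nothing, so the contrast is tested at 5%.
2. Tukey over the four means. The 5% critical value of the studentized range for 4 means and 104 degrees of freedom is 3.69. Dividing by √2 gives a t value of 2.61, which is a two-sided level of 0.0104 for any one contrast.

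**Chance of at least one false arm difference**

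There is one arm contrast per parameter. With independent parameters the formula is 1 − (1 − α)^m. For example:
- 1 − 0.95^12 = 46%
- 1 − 0.95^24 = 71%
- 1 − 0.9896^12 = 12%
- 1 − 0.9896^24 = 22%

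With a common correlation of 0.7, the probability comes from integrating over the shared component of equicorrelated normal test statistics. Simulation of the 5% case at 27 per arm agrees for 12, 24 and 100 parameters.

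| Parameters (m) | 5% per contrast, independent | 5%, correlation 0.7 | Tukey over four means, independent | Tukey, correlation 0.7 |
|---|---|---|---|---|
| 12 (diffusion) | 46% | 23% | 12% | 6% |
| 24 (diffusion by side) | 71% | 31% | 22% | 9% |
| 50 (assumed areas) | 92% | 40% | 41% | 13% |
| 100 (assumed areas) | 99% | 50% | 65% | 17% |

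The expected number of false arm differences does not depend on the correlation. For 100 parameters it is 100 × 0.05 = 5 on the first reading and 100 × 0.0104 = 1.0 on the second.

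The independent columns are upper bounds. The diffusion indices are related by construction: mean diffusivity is (axial + 2 × radial)/3.

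**The case against.** The best defence is that Tukey is not misapplied. Section 9.2 attaches it to an ANOVA of two groups before and after treatment, which is the setting it is made for. What is absent is a further rule across regions, and such a rule is often left to a statistical or imaging analysis plan, which is not at hand. The first half of this stands: Tukey is sound for contrasts within one parameter. The second half does not fully answer the point. Section 9.2 is not silent, because it names its correction and fixes 5% for every listed test. A later plan that added control across regions would have to depart from that rule.

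The defence also limits the size. Figures at 5% per contrast ignore Tukey. If Tukey runs over four means and the parameters correlate at 0.7, the countable diffusion set gives 6% to 9%, close to the nominal level.

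Three stronger readings are tempting, and the protocol supports none of them.
- A reader might infer that the secondary objective cannot be answered. Sections 2 and 5.5 ask mainly about association, which section 9.2 examines by Pearson correlations of PEV and PERG parameters with the imaging measures. The MRI arm comparisons only support that question.
- A reader might infer that about 27 patients per arm makes false findings more likely. The type I error of a valid test does not depend on the sample size.
- A reader might infer that Tukey should be replaced. Dropping it without naming a single contrast would remove the protection among the arm-by-time means.

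**Conclusion.** The point holds as a matter of error control across parameters. The protocol fixes Tukey and a 5% rule for a wide set of MRI arm comparisons, and neither limits the family-wise error over that set.

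For the diffusion parameters, the chance of at least one false arm difference lies between 6% and 46% for 12 parameters and between 9% and 71% for 24. For an assumed 100 areas it lies between 17% and 99%. The low ends take Tukey over four means with correlation 0.7; the high ends take 5% per contrast with independence. Every case exceeds 5%, but how far depends on how Tukey is applied and on a correlation that the protocol does not give. Only the count of 12 comes from the protocol.

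The primary RCT comparison and the sample size are untouched. This is worth correcting, but it does not threaten the trial's main result.

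**What to change.** Amend section 9.2 as follows:
1. Name one between-arm contrast per MRI parameter, for example the difference between arms in change from T1 to T3.
2. Keep Tukey's method only for arm-by-time contrasts within a parameter.
3. Define the MRI family for the secondary objective as the LGN (NGL), optic tract and visual cortex measures, and control the false discovery rate or family-wise error at 5% across it. For scale, Bonferroni over 12 parameters would mean 0.05/12 = 0.0042 each, and over 24 it would mean 0.05/24 = 0.0021.
4. Report whole-brain morphometry and all other networks as exploratory, with voxel- or cluster-level family-wise correction or false-discovery correction.

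The change is in wording and in analysis settings, with no added patients, visits or scans. The cost is that some nominally significant MRI differences will no longer be called significant.

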5.5 Outcomes

The nerve conduction along the post-retinal optical pathways will be determined through the evaluation of the RCT through the simultaneous recording of PERG and PEV, the function of the RGCs will be evaluated through the recording of the PERG, the morphological evaluation of the RGCs will be carried out through the OCT evaluations and the morphological and functional evaluation of the nerve structures that form the optical pathways will be performed by means of Cerebral Magnetic Resonance (MRI).

The primary objective is the assessment of changes in the RCT in patients treated with citicoline in oral solution compared to changes in the RCT assessed in patients treated with placebo.

The secondary objectives will be to evaluate whether the changes in RCT in patients treated with Citicoline in oral solution are associated or not with **morphological and functional changes in the nerve structures that form the optical pathways** (NGL, optic tract, visual cortex) and if both conditions may be related to the morpho-functional variations of the RGCs and of the visual field.

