5.5.1. Psychophysical Evaluations

a) Visual Field (VF)

Static perimetry will be performed for VF measurements (Humphrey, 24-2 and 10-2 SITA Standard Program, with fixation losses, false positive and false negative rates, which should be <20%). The main indices of Humphrey perimetry are: Mean Deviation (MD) and Pattern Standard Deviation (PSD) and Mean Sensitivity (MS). The MD establishes the average of the defect obtained in all the points tested, considers the increasing dispersion of sensitivity values with respect to the data obtained in normal subjects based on the eccentricities and therefore can represent an index of the severity of the global damage. PSD indicates the homogeneity of the distribution of the visual field defect and thus provides information on localized damage. MS is the average of the sensitivity values measured at each probed point.

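### Protocol 9.2 tests the visual field only within each arm: it has no formal comparison with placebo and no place in the correlations that the secondary objective needs

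*Protocol*

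**What the plan says.** Protocol 9.2 opens with a list that includes the visual field under its abbreviation CV: "The data of each group, obtained from the PEV, PERG, CV, OCT and RM measurements will be represented by their mean and standard deviation". Section 2 shows what the abbreviation means, in the phrase "the morpho-functional variations of the RGCs and of the visual field (CV". The next step in 9.2 is a within-arm test that refers back to that list: "For each group, any variations in the measurements indicated above will be evaluated by means of a t-test for paired data".

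The one between-group analysis follows. It says that "the parameters of the electrophysiological, morphological and MRI measurements related to the two groups will be compared pre and post treatment", by ANOVA with Tukey's correction. The correlations then pair PEV and PERG with OCT, with functional MRI connectivity and with diffusion MRI. The section closes by applying the 5% significance level to every test it lists.

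Elsewhere, the protocol places the visual field under the heading "5.5.1. Psychophysical Evaluations", separate from the electrophysiological (5.5.2), morphological (5.5.3) and neuroradiological (5.5.4) evaluations. Section 5.6 makes it an efficacy parameter: "For the assessment of the visual field (HFA 24-2 and 10-2), the following will be considered: MS, MD and PSD". The secondary objective in 5.5, which matches section 2, asks about the RCT changes and the MRI changes, and "if both conditions may be related to the morpho-functional variations of the RGCs and of the visual field".

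**The concern.** Two gaps follow from these lists.

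First, an efficacy parameter of a placebo-controlled trial is left with p-values from inside each arm only. A change within an arm combines any drug effect with practice at perimetry, regression to the mean after selection on mean deviation (4.1 requires -6 to -25 dB), and natural change. If one arm reaches significance and the other does not, that does not show that the arms differ. Under 9.2, however, a within-arm p-value below 5% still counts as significant.

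Second, part of the secondary objective has no analysis. It asks whether RCT and MRI changes are related to visual field changes, and no listed correlation contains a visual field index. This gap does not depend on any assumption about drift.

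The visual field result matters to the reader because the introduction (1.1 and 1.3) cites reduced perimetric progression and visual field improvement with citicoline as part of the background.

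**Working it through.** **1. The lists side by side**

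| Analysis in 9.2 | Electrophysiology | OCT | MRI | Visual field |
|---|---|---|---|---|
| Mean and SD by group | yes | yes | yes | yes |
| Paired t-test within each arm | yes | yes | yes | yes |
| Between-group ANOVA | yes | yes | yes | not named |
| Pearson correlations | yes | yes | yes | not named |

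No other section supplies either missing analysis.

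**2. The number per arm**

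Section 9.1 gives RCT 70.21 ± 9.12 ms and 63.3 ± 8.15 ms, alpha 5%, power 80%, and 27 per group.

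- Difference: 70.21 - 63.3 = 6.91 ms.
- Pooled SD: √((9.12² + 8.15²)/2) = 8.65 ms.
- Two-sided, two-sample: n = 2 × (1.960 + 0.842)² × 8.65² / 6.91² ≈ 24.6, so 25 per group (26 with the t distribution). A paired t-test with zero correlation gives 27.
- Dropout: 27 / 0.90 = 30.

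The stated 27 reproduces to within two patients, and 27 is used below as the evaluable number per arm.

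**3. What within-arm testing can produce with no drug effect**

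The documents give neither a drift nor an SD of change for the visual field, so the drift is an assumed range. Let k be the mean change towards improvement divided by the SD of within-patient change. It is the same in both arms, the arms are independent, there is one value per patient, and tests are two-sided at 5% (9.2 does not state sidedness).

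- p = P(significant improvement in one arm) = P(T > 2.056), where T is noncentral t with 26 degrees of freedom and noncentrality k√27.
- P(citicoline significantly improved, placebo not) = p(1 - p).

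Example at k = 0.4: noncentrality 0.4 × 5.196 = 2.08; p = 0.517; p(1 - p) = 0.517 × 0.483 = 0.250.

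| k | p, one arm | Citicoline alone |
|---|---|---|
| 0 | 2.5% | 2.4% |
| 0.1 | 7.2% | 6.7% |
| 0.2 | 16.9% | 14.0% |
| 0.3 | 32.3% | 21.9% |
| 0.4 | 51.7% | 25.0% |
| 0.5 | 70.6% | 20.8% |
| 0.6 | 85.1% | 12.7% |
| 0.8 | 97.9% | 2.0% |

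With 30 per arm the pattern is the same: 2.4% at k = 0, about 25% near k = 0.4, 1.1% at k = 0.8.

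**4. The comparison that is missing**

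In a test of citicoline change minus placebo change, a common drift cancels. The false-positive rate in favour of citicoline is 2.5% per parameter at every k.

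**The case against.** **It may be loose drafting.** The section is headed as general methodology, its opening list includes the visual field, and nothing says that the visual field will not be compared. A statistical analysis plan that is not shown could add the test. This stands in part. But the protocol is not silent: it gives one list with the visual field and then a narrower one without it. A plan written to that text would carry the gap forward.

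**No objective requires an arm comparison of the visual field.** This is correct. The primary objective is RCT, which is electrophysiological and covered by the ANOVA, and the secondary objective is an association. The missing correlation is therefore the more direct mismatch with the objectives. The case for an arm comparison rests on 5.6, which names the visual field indices as efficacy parameters.

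**The placebo arm is unused.** A reader might infer this, but 9.2 does not support it: both arms are summarised and both get the paired test. Only the formal comparison between them is absent.

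**The trial will present a within-arm change as a citicoline benefit.** A reader might infer this too. No section says so, and the expected results in 10.1 claim no visual field benefit. The text supports only that such a result could be reported that way.

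**The risk is already reduced.** Perimetry is done at both T0 and T1, reliability limits are set in 5.5.1, patients come from a cohort followed for at least 12 months (section 6), and the entry limits are two-sided, so regression effects partly oppose each other. Learning and progression also pull in opposite directions, so a net drift near zero is plausible. All of this lowers the risk and none of it removes it.

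**A larger figure is tempting.** The chance that exactly one arm is significant can reach 50%, but that counts placebo-only results as well. The quantity that bears on a false citicoline claim is citicoline alone, which cannot exceed 25% on these assumptions.

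**Conclusion.** The gap is real and secondary. As written, the visual field has no formal comparison with placebo, and the visual field part of the secondary objective has no analysis. Both statements rest on the text alone.

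The size of the first gap depends on a drift that the documents do not give. Citicoline-alone significance without a drug effect ranges from about 2% to 25%, and is no worse than nominal when there is no drift or when drift is so large that both arms are almost always significant. These figures assume equal drift in both arms, 27 evaluable patients per arm, one value per patient and two-sided 5% tests. They are a range and not an estimate of what will happen in this trial.

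**What to change.** In Protocol 9.2:

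- Add visual field MS, MD and PSD to the between-group analysis, as a comparison of change from T1 to 12 months, preferably adjusted for the T1 value. The adjustment is a preference; the comparison between arms is the necessary part.
- State that the within-arm paired tests are descriptive and are not evidence of a treatment effect.
- Add the correlation of RCT change, and of MRI change, with change in visual field MD.

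The cost is a short edit. Section 5.2 already schedules perimetry at all four visits, so no new data are needed. The downside is more secondary tests: three indices on two programs make six between-group comparisons at an unadjusted 5%. They should be labelled secondary or exploratory, for example with 24-2 MD named as the main one.
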